11.10.7 Confirmation Measurement

Confirmation of CR and PR is required and must occur no fewer than 4 weeks after initial documentation of CR or PR. If CR is pending confirmation and is designated at an assessment followed by 1 or more NE assessments, and/or PR assessments such that the Target Lesion Response is CR and the Non-Target Lesion Response is NE, CR may be confirmed thereafter if Non-Target Lesion Response returns to CR. Similarly, if a PR is pending confirmation and is designated at an assessment followed by 1 or more NE and/or SD assessments, PR may be confirmed thereafter. Subsequent Target Lesion Responses following a CR are limited to CR, PD or NE; PD for target lymph nodes is met only if any lymph node target lesion reaches a short axis measurement of ≥ 15 mm.

11.11 Appendix 11. Specific Guidance for Cytokine Release Syndrome, Immune-effector Cell-associated Neurologic Syndrome, and Tumor Lysis Syndrome

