3.2 Sample Size

Approximately 30 subjects will be enrolled in the study. With 30 subjects enrolled at the target dose, the probability that the observed ORR will be greater than **different thresholds are presented in Table 3.2-1.**

Table 3.2-1. Probabilities of Observed ORR Greater Than Thresholds With Sample Size of 30

True ORR	Probability of Observed ORR > 25 %	Probability of Observed ORR > 30%
0.35	88%	64%
0.4	96%	82%

With 30 subjects, there is a 79% to 96% probability of observing at least 1 adverse event if the true event rate is 5% to 10%.

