5.2 Efficacy Endpoint-related Definitions

Best Overall Response (BOR)

The subject's best response assignment depends on the findings of both target and non-target disease and also takes into consideration the appearance of new lesions and confirmation of response based on the findings from MRI/CT scans. Confirmation of progressive disease is not required. BOR is based on all post-baseline disease assessments that occur prior to the initiation of subsequent anticancer treatment. At least 5 weeks from the first dose of IP must elapse without radiological disease progression to meet the minimum criteria for SD duration in order to assign a BOR of SD. In general, subjects not classifiable under the RECIST 1.1 response categories due to inadequate data or early death are classified as not evaluable (NE) for BOR but will be counted in the denominator of all response rate calculations. BOR per RECIST 1.1 has the following possible categories: complete response (CR), partial response (PR), stable disease (SD), progressive disease (PD), not evaluable (NE). The rules for deriving the BOR are detailed in Appendix B.

Objective Response (OR)

OR is defined as a BOR of CR or PR per RECIST 1.1. Subject without a post-baseline tumor assessment is considered non-responder.

Objective Response Rate (ORR)

ORR is defined as proportion of subjects with BOR of CR or PR per RECIST 1.1.

Disease Control (DC)

DC is defined as a BOR of CR or PR or SD per RECIST 1.1.

Disease Control Rate (DCR)

DCR is defined as proportion of subjects with a BOR of CR or PR or SD per RECIST 1.1.

Duration of Disease Control (DoDC)

DoDC is defined as time from **the date of first dose of tarlatamab** until the first documentation of disease progression or death due to any cause, whichever occurs first. Only subjects with a BOR of confirmed response (CR/PR) or SD are evaluated for DoDC.

DoDC (Months) = (earlier of progressive disease date or death date – **date of first dose of tarlatamab** + 1) × 12 / 365.25

DoDC is censored following the same censoring rules as PFS ([Appendix C](#)).

Duration of Response (DOR)

DOR is defined as time from first documentation of CR or PR per RECIST 1.1 until the first documentation of progressive disease or death due to any cause, whichever occurs first. Only subjects who with a BOR of confirmed response (CR/PR) are evaluated for DOR.

DOR (Months) = (earlier of progressive disease date or death date – response start date + 1) × 12 / 365.25

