Appendix B. BOR per RECIST 1.1

BOR by investigator will be derived based on the timepoint response collected in the RECIST 1.1 CRF. BOR by central review will be derived from timepoint response shared by the central imaging vendor. At each time point, BOR will be derived based upon the evaluated timepoints up to and including the current MRI/CT assessment. The following rules will apply to BOR:

- CR is better than PR is better than SD is better than PD is better than NE
- For a BOR of SD, a duration of ≥ 35 days since the cycle 1 day 1 is required
- For a BOR of CR or PR confirmation is required. PR can be confirmed by a PR or CR. The confirmation assessment must be in a consecutive assessment ≥ 28 days after the initially observed assessment of CR or PR except the following cases:
 - An unlimited number of intermittent assessments of NE or CR <28 days can occur between the initial response and the confirmation of CR. For example, BL, CR, NE, NE, NE, CR – the CR at post-baseline 1 is confirmed at post-baseline 5. SD is not allowed between CR and subsequent confirmation CR.
 - An unlimited number of intermittent assessments of NE, SD, PR or CR <28 days can occur between the initial response and the confirmation of PR. For example, BL, PR, SD, SD, SD, PR – the PR at post-baseline 1 is confirmed at post-baseline 5.

[Table 14-2](#) provides the BOR determination per RECIST 1.1 where confirmation of response (CR/PR) is required. [Table 14-3](#) outlines the steps to derive Confirmed_BOR (step 1) given timepoint assessments.

At interim analyses (if any), due to lack of sufficient follow-up time for confirmation scan, study team may choose to report both confirmed responders and unconfirmed responders (subjects had an initial PR or CR and still has potential for future confirmative scans). Interim_BOR is defined to include unconfirmed responders in addition to those who achieve Confirmed_BOR. [Table 14-3](#) step 2 provides details to derive the unconfirmed responders.

Table 14-2. BOR per RECIST 1.1 where Confirmation of CR/PR is Required

Criterion	Timepoint T1 Response	T1 ≥ 35 days after C1D1?	Timepoint T2 Response	T2 ≥ 35 days after C1D1?	T2 ≥ 28 days after T1?	BOR_temp
C1	CR	Yes	CR	-	Yes	CR
C2			CR	-	No	SD
C3			PR, SD	-	-	Query data*

C4			PD	-	-	SD
C5			NE, No further evaluations			SD
C6		No	CR	-	Yes	CR
C7			CR	Yes	No	SD
C8			CR	No	No	NE
C9			PR, SD	-	-	Query data*
C10			PD	-	-	PD
C11			NE, No further evaluations			NE
C12	PR	Yes	CR, PR	-	Yes	PR

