C13			CR, PR	-	No	SD
C14			SD	-	-	SD
C15			PD	-	-	SD
C16			NE, No further evaluations			SD
C17		No	CR, PR	-	Yes	PR
C18			CR, PR	Yes	No	SD
C19			CR, PR	No	No	NE
C20			SD	Yes	-	SD
C21			SD	No		NE
C22			PD	-	-	PD
C23			NE, No further evaluations			NE
C24	SD	Yes	CR, PR, SD, PD, NE, no more evaluation			SD
C25		No	CR, PR, SD	Yes	-	SD
C26			CR, PR, SD	No	-	NE
C27			PD	-	-	PD
C28			NE, No further evaluations			NE
C29	PD		-			PD
C30	NE	-	NE, No further evaluations			NE
C31		-	CR, PR, SD	Yes	-	SD
C32		-	CR, PR, SD	No	-	NE
C33		-	PD	-	-	PD

*If a CR is truly met at first time point, then any disease seen at a subsequent time point, even disease meeting PR criteria relative to baseline, makes the disease PD at that point (since disease must have reappeared after CR). Best response would depend on whether minimum duration for SD was met. However, sometimes 'CR' may be claimed when subsequent scans suggest small lesions were likely still present and in fact the patient had PR, not CR at the first time point. Under these circumstances, the original CR should be changed to PR. A CR may also be followed by a PR when the target lesion assessment is CR and the non-target lesion assessment is NE. In both of these situations, the best response is PR.

Table 14-3. BOR Derivation Step

Step 1. Derive Confirmed_BOR at each visit

Derive Confirmed_BOR at each visit:

- i) At Visit 1: Use the Visit 1 scan result and refer to [Table 14-2](#) to derive Confirmed_BOR.
- ii) At Visit 2 onward:
 - (a) If current visit is CR: Find last scan that is not NE and at least 28 days before current visit. If current visit is PR: Find last scan that is not NE or SD and at least 28 days before current visit. Derive BOR_temp as below:

Last scan	Current	BOR_temp
CR	CR	CR
PR	CR	PR
PR	PR	PR

- b) If none of above fits, find last scan reference [Table 14-2](#) to derive BOR_temp.

Current visit Confirmed_BOR = best of (BOR_temp, last visit confirmed_BOR). Use rule CR > PR > SD > PD > NE

Step 2. Derive Interim_BOR at last visit prior to DCO	

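### Read literally, SAP Table 14-3 turns CR–NE–PR into stable disease even where its own footnote gives PR, and CR–PR (non-target NE)–CR into PR where Protocol 11.10.7 allows CR

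*SAP*

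**What the plan says.** SAP 5.2: "ORR is defined as proportion of subjects with BOR of CR or PR per RECIST 1.1". A subject with BOR of SD is therefore a non-responder, and is also outside the duration of response (DOR) analysis.

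SAP Appendix B, Table 14-3, Step 1(ii), derives BOR at each visit from the second onward:

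- **Step (a), current scan CR:** "Find last scan that is not NE and at least 28 days before current visit".
- **Step (a), current scan PR:** "If current visit is PR: Find last scan that is not NE or SD and at least 28 days before current visit".
- The pair found is looked up in three rows: CR then CR gives CR; PR then CR gives PR; PR then PR gives PR.
- **Step (b):** "If none of above fits, find last scan reference" Table 14-2.
- The running value is the better of the new result and the previous visit's value, ranked CR, PR, SD, PD, NE.

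In Table 14-2, a CR followed by a PR or SD (rows C3 and C9) yields a data query. Its footnote distinguishes three cases:

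1. A true CR followed by any disease is PD at that scan, and best response depends on the minimum SD duration.
2. A CR claimed in error is changed to PR.
3. A PR can follow a CR because target response is CR and non-target response is NE.

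Of the last two it says: "In both of these situations, the best response is PR".

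Protocol 11.10.7 covers a pending CR followed by NE assessments, by PR assessments with target CR and non-target NE, or by both: "CR may be confirmed thereafter if Non-Target Lesion Response returns to CR". The Appendix B text allows only NE, or a CR less than 28 days on, between a CR and its confirmation.

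**The concern.** The three-row table in step (a) omits CR followed by PR. When the two scans are adjacent, step (b) still reaches the C3/C9 query and its footnote. When an NE lies between them, the fallback pairs the PR with the NE, and neither the query nor the footnote comes into play. A subject whom the footnote would call PR is then counted as a non-responder in the primary endpoint and left out of DOR.

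Separately, the look-back for a current CR skips NE scans but not the PR scans that Protocol 11.10.7 tells the analyst to look past. SAP Section 10 lists changes from the protocol and does not mention this one.

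If such a case turned up at analysis, someone would have to choose its classification after seeing the data, on the primary endpoint of a study of about 30 subjects.

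**Working it through.** **The plan's own figures.** "Approximately 30 subjects will be enrolled in the study" (SAP 3.2). With X ~ Binomial(30, p), an observed ORR above 25% means X ≥ 8, and above 30% means X ≥ 10.

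| True ORR | P(X ≥ 8) | Stated | P(X ≥ 10) | Stated |
|---|---|---|---|---|
| 0.35 | 87.6% | 88% | 64.2% | 64% |
| 0.40 | 95.7% | 96% | 82.4% | 82% |

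These reproduce and are not in dispute.

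**Trace of CR–NE–PR.** Scans are at nominal days 42, 84 and 126 (every 6 weeks, Protocol 1.3).

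| Visit | Scan | Step | BOR_temp | Running BOR |
|---|---|---|---|---|
| 1 | CR | Table 14-2, C5 ("NE, No further evaluations") | SD | SD |
| 2 | NE | (b): last scan CR, C5 | SD | SD |
| 3 | PR | (a): finds the CR 84 days earlier, no matching row; (b): last scan NE, C31 | SD | **SD** |

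With scans at days 30, 72 and 114, so that the first falls before day 35, the path is C11 (NE), C11 (NE), C31 (SD). The final result is again SD.

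**Trace of CR–PR–CR, where the PR is target CR with non-target NE.** Visit 1 gives SD (C5). Visit 2 gives the C3 query, which the footnote resolves to PR. At visit 3 step (a) stops at the PR, matches the PR-then-CR row and returns **PR**. Protocol 11.10.7 permits a confirmed CR.

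**Other sequences run through the same rules:**

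- PR–NE–PR gives PR and CR–NE–CR gives CR, so an intervening NE alone does no harm.
- CR–NE–PR–PR and CR–NE–PR–CR both give PR, so a later PR or CR scan repairs the result.
- CR–NE–PR–PD stays SD.
- If step (b) is changed to look back past NE, CR–NE–PR reaches the C3 query, and the footnote decides.

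**Size per subject.** One subject is 1/30 = 3.3 points. With Clopper-Pearson 95% intervals, 11/30 = 36.7% (19.9 to 56.1) and 12/30 = 40.0% (22.7 to 59.4).

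**How many subjects.** The documents give no CR rate. As an assumption, let 1% to 10% of subjects have a CR scan (0.3 to 3 of 30), and let 5% to 15% of those have an NE or non-target-NE scan next. The product runs from 0.3 × 0.05 = 0.015 to 3 × 0.15 = 0.45 subjects. For sequence (1) this is too high on these inputs: it ignores the further needs for a PR afterwards and no later CR or PR, and it includes sequence (2), which cannot move ORR.

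**The case against.** The best defence is that the last scan in step (b) may mean the last non-NE scan, as the column of the same name does in step (a) once the skipping is done. On that reading CR–NE–PR reaches C3 and the footnote. The rows with NE as the first time point (C30 to C33) do not rule it out, since they are still needed when every earlier scan is NE. This has some force, but step (b) states no such exclusion, and a programmer following the text would use the NE. Two defensible readings that give different responder counts are reason enough to settle the wording.

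The defence is right against several stronger readings a reader might infer:

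- *That the SAP has no route at all for CR followed by PR.* It does: C3/C9 with the footnote handle adjacent scans. The gap is in the step (a) table, and it bites when an NE intervenes.
- *That the footnote always gives PR.* It does not. A true CR followed by disease is PD at that scan, and the BOR is then SD or PD; Protocol Table 11-6 and its footnote agree. For such a subject the derived SD can be correct, so the error does not always run one way.
- *That any CR followed by one unreadable scan is lost.* CR–NE–CR gives CR, and a later PR or CR also rescues CR–NE–PR.
- *That both sequences move ORR.* Sequence (2) gives PR instead of CR, and both are responders.

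Against the defence, Protocol 11.10.7 limits target lesion responses after a CR to CR, PD or NE. A PR that remains after a CR in reads that follow the rules therefore points mainly to the two cases in which the footnote gives PR.

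**Conclusion.** The point holds in a narrow form. On the literal text, Step 1(ii) gives results that conflict with the documents' own rules for two rare sequences, and the two conflicts are separate:

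1. CR–NE–PR with no later CR or PR becomes SD. This conflicts with the Table 14-2 footnote when the CR needed relabelling or the PR comes from non-target NE. It does not conflict with it when a true CR has relapsed. Only this sequence can move ORR, by 3.3 points per subject.
2. CR–PR (target CR, non-target NE)–CR becomes PR. This conflicts with Protocol 11.10.7 and is not declared in SAP Section 10. It changes only the split between CR and PR.

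The expected number of affected subjects cannot be derived from the documents and is probably well below one. The case for acting rests on where the gap sits, in the algorithm for the primary endpoint, and on the low cost of closing it before the data are seen. It does not rest on a likely material shift in the result. The first conflict assumes that step (b) is programmed as written, with NE scans counted as the last scan.

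**What to change.** Amend SAP Appendix B before database lock:

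1. In Step 1(ii), when the current scan is PR and the look-back past NE and SD finds a CR, send the case to C3/C9, not C31. Resolve it by the footnote's three cases: PR if the CR is relabelled as PR, or if the PR is target CR with non-target NE; otherwise PD at that scan, with BOR of SD or PD according to the minimum SD duration. Do not add an unconditional row making CR then PR equal to PR, because it would count a relapse after a true CR as a confirmed response. Such a row would also leave CR–PR–CR at PR.
2. When the current scan is CR, let the look-back also skip PR scans with target CR and non-target NE, and add these to the assessments allowed between a CR and its confirmation. If the sponsor prefers the present rule, list the departure from Protocol 11.10.7 in SAP Section 10.
3. Keep the C3/C9 query, including for CR then SD, but state how it is resolved when the reads come from the central reviewers. A query has no place in the ranking that sets the running value.

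The cost is a few lines of SAP text and programming, with no new scans. The one dependency is that the vendor transfer must carry the target and non-target components of the central reads. Appendix B mentions only time point responses, so this should be checked.

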Appendix C. PFS Censoring Rules

Situation up to DCO/EOS	Date of Event or Censor	Outcome
No evaluable post-baseline tumor assessments, no death recorded	Date of first dose date of IP	Censor
PD	Date of first detection of PD	Event
No PD, but death recorded	Date of death	Event
Start of new anti-cancer therapy prior to any PD or death	Date of last evaluable tumor assessment before or on start of new anti-cancer therapy	Censor
No PD, no death recorded, no start of new anti-cancer therapy	Date of last evaluable tumor assessment	Censor
Death or PD immediately after 2 or more missed tumor assessment (14 weeks)	Date of last evaluable tumor assessment prior to the first missing assessment ^a	Censor

^a This supersedes the previous rules that result in PFS event at date of PD or death.
